### 2. Background

#### ***Rigor of prior research: Cardiorespiratory failure patients suffer from persistent psychological distress—as COVID-19 patients likely will.***

>2 million patients are treated in ICUs annually in the US for cardiorespiratory failure caused by pneumonia, sepsis, and congestive heart failure, among others. After discharge, patients experience clinically important symptoms of psychological distress—depression, anxiety, and post-traumatic stress disorder (PTSD)—symptoms that are both common (50-70%) and persistent. Pneumonia, the second-most common cause of hospitalization, places its survivors at high risk for persistently worsened health status and lasting depression, anxiety, and PTSD symptoms. Currently acute infection with the severe acute respiratory syndrome novel coronavirus 2 which leads to coronavirus disease 2019 (COVID-19) is causing the largest pandemic of pneumonia in over 100 years. COVID-19 is a mild disease for ~80% of patients, but 10-20% of patients are hospitalized with pneumonia. Of those hospitalized, up to 88% require respiratory support such as mechanical ventilation. COVID's specific post-hospital outcomes have not been clearly described; not even 100 days have transpired since the disease was first defined. Yet since patients will be recovering from severe disease during a global state of emergency and economic stress, COVID-19 likely puts them at even higher risk of distress than other forms of cardiorespiratory illness.

#### ***Conceptual orientation and rigor of proposed research: The LIFT mobile mindfulness intervention is a scalable approach for improving COVID-19 patients' psychological distress.***

The COVID-19 pandemic represents a unique threat to patient-centered care given new norms of 'social distancing,' limited healthcare resources that serve as barriers to distress assessment and timely treatment, and economic devastation of those impacted by it. Clinical resources are stretched thin as health systems are overwhelmed with the stresses of caring for massive numbers of COVID-19 patients, forcing the cancellation of outpatient clinics. Most research institutions have banned study staff from conducting clinical research that includes direct patient contact. These barriers require a novel approach that we believe can be effectively provided by this Supplement proposal.

LIFT is ideally positioned to overcome barriers to both the timely delivery of mind-body therapy as well as research participation during a pandemic like COVID-19. Its tested mindfulness content promotes a practice of non-judgmental awareness that can alleviate distress by uncoupling emotional reactions and habitual behavior from unpleasant symptoms, thoughts, and emotions—content that improves symptoms of depression, anxiety, and PTSD. LIFT's 'touchless deployment' allows automated screening, consenting, intervention activation, and data collection without direct patient contact. Additionally, LIFT is a self-guided mobile app that works on any device, giving it the flexibility and scalability required in a pandemic. LIFT is a scalable solution for overcoming barriers to addressing COVID patients' distress—and our research network is ideal for conducting an RCT to test it.

### 3. Focus of the Study and Specific Aims

#### ***BLUE CORAL and LIFT COVID study designs (Figure)***

**LIFT COVID** is a 300-participant, two-arm, parallel groups RCT with 6-month follow up nested within the NHLBI PETAL Network's **BLUE CORAL** observational study of patients hospitalized with cardiorespiratory manifestations of COVID-19. The PETAL data coordinating site, the University of Michigan, will screen participants, conduct informed consent, and conduct all follow up interviews. Participants with symptoms of depression (PHQ-9  $\geq 5$ ) 1 month after hospital discharge will be randomized to either the LIFT intervention (Standard Dose, App-based Symptom Response, No intro

Call) or usual care control. Follow up interviews will be done 1, 3, and 6 months post-discharge (i.e., 0, 2, and 5 months post-randomization), as per BLUE CORAL's current timeline.

### Specific aims for LIFT COVID RCT

**Aim 1:** In an RCT nested within the NHLBI's PETAL BLUE CORAL cohort study of 1,500 planned participants, to test the clinical impact of LIFT (n=150) vs. usual care control (n=150) among recently discharged patients recovering from serious COVID-19 infection.

*Hypothesis:* Compared to control at 3 months post-discharge (i.e., 2 months post-randomization [T2]), LIFT will reduce symptoms of depression (primary outcome; Patient Health Questionnaire-9 [PHQ-9] as well as secondary outcomes of anxiety (General Anxiety Disorder [GAD-7]) and PTSD (Post Traumatic Stress Scale [PTSS]).

**Aim 2:** In an RCT nested within the PETAL BLUE CORAL cohort study, to test the clinical impact of LIFT (n=150) vs. control (n=150) at 6 months post-discharge.

*Hypothesis:* Compared to control, LIFT will reduce symptoms of depression, anxiety, and PTSD and 6 months post-discharge.

**Aim 3:** Among RCT intervention participants, explore barriers and facilitators to LIFT intervention implementation and dissemination in the context of a pandemic.

*Approach:* Using qualitative analysis of semi-structured interviews from 25 purposively sampled participants enrolled from Supplement Aim 1, we will explore perceptions about barriers to accessing, using, and applying LIFT effectively in a pandemic. This could improve LIFT processes in the future.

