## **7. Data Collection**

### **7.a. BLUE CORAL data collection**

BLUE CORAL includes data collection from enrolled patients' clinical records. There are three types of forms for each study: admission (hospital / study day 1), daily, and discharge.

The case report form (CRF) is built in REDcap which can be imported as a local instance or centrally through the PETAL CCC. Since there may be times when study personnel are mandated to work from

home due to the ongoing pandemic, BLUE CORAL has many study procedures that are designed to allow off-site completion. All elements that contribute to the COVID ordinal outcome scale are included in daily and summative data collection. Manual data entry of all elements into REDCap may not be required depending on the site's ability to extract data from the EMR.

The BLUE CORAL study will obtain pre-hospital information from patients or their caregivers before hospital discharge. The survey consists of questions regarding functional status and health-related quality of life. PETAL study staff members are familiar with the conduct of these surveys as they were used successfully in the ROSE RCT. With high severity of illness, infection control precautions, and absence of family visitation, we anticipate that survey completion will be difficult. Therefore, we have developed multiple approaches to survey completion (telephone, tablet computer, or email with either patients or families) and will attempt to complete as able.

BLUE CORAL patients who survive hospitalization, speak English, are domiciled, and did not have severe dementia or severe disability before hospitalization may be eligible to enter the post-hospital follow-up study (BLUE CORAL). This study will be conducted by the FUNCTION team at the University of Michigan, led by [name], using protocols developed and executed in the PETAL Network ROSE and ongoing CLOVERS studies. Sister sites, Oregon Health & Sciences University (OHSU) and University of Colorado-Denver, led by Drs. [name] and [name], respectively, may be asked to conduct the study visits as needed. Post-hospital follow-up will occur by telephone at 1, 3 and 6 months after hospital discharge (Table 1). Patients will provide consent for continued involvement at the time of the first call.

Table 1: Data collection timing and content for BLUE CORAL and LIFT RCT participants.					
	Hospital	1 month* (T1)	During intervention 	3 months* (T2)	6 months* (T3)
Contact info	X	X		X	X

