PHQ-9 depression (primary outcome)		X	X	X	X
GAD-7 anxiety		X		X	X
EQ-5DL quality of life	X	X		X	X
ADL / IADL limitations	X	X		X	X
Financial strain	X	X		X	X
Cardiopulmonary symptoms		X		X	X
Cognitive function (MOCA/AD8, Hayling)		X		X	X
Rehospitalization		X		X	X

\* Timing is from the time of hospital discharge  
1 Collected via the Lift mobile app weekly  
2 These data collected only for LIFT RCT participants. This will be done via the app platform.

These post-hospital assessments will allow BLUE CORAL to measure the levels and rates of recovery on cardio-pulmonary symptoms as well as the key domains outlined in the NHLBI R24-funded “Improving Long-Term Outcomes” Program; to determine risk factors associated with poor outcomes; to assess the burden of COVID-19 recovery primary spouse or family caregiver of cohort members, stratified by whether the spouse themselves had COVID-19 or not; and to evaluate the association of the COVID-19 Outcome Score with patient- centered outcomes.

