### 7.b. LIFT COVID Surveys

As shown in Table 1, participants enrolled in the LIFT COVID intervention arm will also complete the PHQ-9 survey weekly within the LIFT mobile app for the duration of the 4-week intervention.

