### 7.c. List of all BLUE CORAL and LIFT COVID surveys

#### Inpatient

- Recent living status (1 item)
- Days hospitalized in month prior to COVID-19 admit (1 item)
- EQ-5D-5L baseline (5 items)
- Activities of Daily Living (ADLs) and Instrumental ADLs baseline (13 items)
- AD8 (8 items, completed by caregiver)
- Household Financial Strain (7 items)
- Occupation and Industry (2 items)
- Number of People in Household (1 item)

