#### Post-hospital patient surveys

[figure not shown]
- COVID-19 Recovery (1 item)
- EQ-5D-5L (5 items)
- Activities of Daily Living (ADLs) and Instrumental ADLs (13 items)
- Financial Toxicity (12 items)
- Cardiopulmonary symptoms and respiratory support (13 items)
- Patient Health Questionnaire-9 (9 items)
- Generalized Anxiety Disorder-7 (7 items)
- Healthcare utilization (1 item)
- Demographics (2 items)
- Montreal Cognitive Assessment MOCA-Blind
- Hayling Test of Executive Function
- Select Current Medications, matched to those collected in-hospital

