## **10. Statistical design, analyses, sample size, and power:**

### ***Aims 1 and 2***

The goal of the parent U01 trial analysis is to determine which LIFT components (i.e., factors) have the greatest salutary effects on MOST optimization criteria of feasibility, usability, and clinical impact.

Analyses for the LIFT COVID RCT's Aims 1 and 2 are designed to compare the clinical impact on psychological distress symptoms (depression, anxiety, PTSD) LIFT (n=150) vs. control (n=150) among COVID-19 patients. All participants will be analyzed by their assigned group, regardless of adherence or crossover status. Briefly, we will test the primary study hypothesis that the PHQ-9 score is lower (i.e., fewer depression symptoms) for LIFT recipients compared to control 3 months post-discharge with a general linear model using SAS PROC MIXED (SAS Institute, Cary NC). An unstructured covariance matrix will be specified to account for the correlation between longitudinal repeated measures. Similar analyses will be performed in Aim 2 for the GAD-7 and PTSS, as well as for all other outcomes at 3 and 6 months. Procedures for missing data will include (as needed) sensitivity analyses, multiple imputation PROC MI, and estimates combined using Rubin's rules as implemented in PROC MIANALYZE.

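### The PTSS is a secondary outcome with a planned analysis and a DSMB review, but no PTSD instrument appears in the data-collection schedule or the survey list

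*Combined protocol and SAP*

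**What the plan says.** Four places in the combined protocol and SAP rely on PTSD data.

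- **Section 3, Specific aims.** Aim 1 lists "secondary outcomes of anxiety (General Anxiety Disorder [GAD-7]) and PTSD (Post Traumatic Stress Scale [PTSS" alongside the PHQ-9 for the comparison at 3 months after discharge. The Aim 2 hypothesis is that "LIFT will reduce symptoms of depression, anxiety, and PTSD and 6 months post-discharge".
- **Section 10, Aims 1 and 2.** "Similar analyses will be performed in Aim 2 for the GAD-7 and PTSS", and all other outcomes are analysed in the same way at 3 and 6 months.
- **Section 17, DSMB.** PTSS scores are among the metrics reviewed at each meeting.
- **Section 15, Reporting Procedures.** Alert values for PTSD symptoms are to be known, in all groups, as soon as a questionnaire is completed.

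Three places set out what is collected.

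- **Section 7.a, Table 1** is titled "Data collection timing and content for BLUE CORAL and LIFT RCT participants".
- **Section 7.b** says that intervention participants "will also complete the PHQ-9 survey weekly within the LIFT mobile app for the duration of the 4-week intervention". It adds no other instrument.
- **Section 7.c** is headed "List of all BLUE CORAL and LIFT COVID surveys". Its post-hospital list includes the PHQ-9 and "Generalized Anxiety Disorder-7 (7 items)", but no PTSD scale.

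**The concern.** An outcome that is hypothesised, analysed and monitored needs a stated instrument, visit and arm. The PTSS has none of these in Section 7, and no version or item count is given anywhere. The GAD-7, named in the same sentence of Aim 1, is scheduled at T1, T2 and T3 and listed with its item count. The plan is therefore inconsistent with itself, and more than a detail is missing.

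Staff working only from the written schedule would collect no PTSS. Symptom scores not taken at 1, 3 and 6 months cannot be recovered later. The PTSD hypotheses could then not be tested, the DSMB would lack one of its listed metrics, and the PTSD alerts would have no source.

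**Working it through.** The plan gives no figure to reproduce on this point. The check compares every place that uses PTSD data with every place that says what is collected.

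**Step 1. Entries in the collection sections.**

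| Place | Entries | PTSD instrument | PHQ-9 | GAD-7 |
|---|---|---|---|---|
| Table 1 (7.a) | 9 | 0 | yes | yes |
| 7.b, LIFT additions | weekly in-app PHQ-9 only | 0 | yes | no |
| 7.c, inpatient | 8 | 0 | no | no |
| 7.c, post-hospital | 12 | 0 | yes | yes |

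The 9 rows of Table 1 are contact information, PHQ-9, GAD-7, EQ-5D, ADL/IADL, financial strain, cardiopulmonary symptoms, cognitive function and rehospitalisation.

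The two lists in which a PTSD scale would be expected are Table 1 and the post-hospital list: 0 of 9 and 0 of 12. Adding the inpatient list gives 9 + 8 + 12 = 29 entries with none. That total carries less weight, because several instruments appear in more than one list and no PTSD outcome is expected in hospital.

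**Step 2. Hypotheses affected.** Aims 1 and 2 name three distress scales at two times: 3 × 2 = 6. PTSD accounts for 1 × 2 = 2 of them. The further outcomes that Section 10 also analyses are outside this count.

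**Step 3. Other routes in the documents.** Section 3 has one site conduct all follow-up interviews on the BLUE CORAL timeline, so those calls are the documented source of outcome data. Section 15 (Privacy) describes email or text links and does not limit them to one arm. Sections 16.b and 18.b mention data gathered outside PETAL or BLUE CORAL. None of these names a PTSD form or visit. They leave another route possible but do not document one.

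**Step 4. What is not affected.** The sample-size statement in Section 10 concerns the PHQ-9 alone. The primary safety measures in Section 17 are adverse events and PHQ-9 scores. If only the T1 PTSS were missing, the randomised comparisons at T2 and T3 would still be valid.

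**Step 5. Volume if the scale is added.** With full retention: 300 × 3 = 900 administrations. With the 40% dropout assumed in Section 10: 300 at T1, 300 × 0.6 = 180 at T2 and at most 180 at T3, so at most 660. The second figure assumes that nobody lost by T2 returns at T3.

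**The case against.** The best counter-argument is that silence in these lists proves little, because they are not exhaustive. Section 7.c omits the C-SSRS item used in the suicidality plan. It also has no survey for the objective in 7.a "to assess the burden of COVID-19 recovery primary spouse or family caregiver of cohort members". Table 1 omits the COVID-19 recovery item and the medications that 7.c lists. In practice, staff work from REDCap interview templates (Section 17), Manuals of Operation and case report forms (Section 16.a), none of which is in these documents. Some figures, including the study-design figure announced in Section 3, could not be seen. Sections 10, 15 and 17 all suggest that the team means to collect the PTSS.

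Much of this stands. The evidence is that the PTSS is unscheduled and unlisted; it does not show that the scale will go uncollected. Loss of a row in text extraction cannot be fully excluded, but it would have to occur in both a table and a separate bulleted list while the PHQ-9 and GAD-7 entries survived in each. The other omissions also differ in kind: neither the C-SSRS item nor a caregiver survey is a named efficacy outcome of this RCT with a planned analysis.

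It is also fair to say that the wording in Sections 15 and 17 looks carried over from another design. Section 17 refers to factor-based groups in a two-arm trial. Section 15 expects frequent telephone contact by the interventionist, although the intervention is self-directed. Those two places are therefore weaker support. The contradiction stands on Sections 3 and 10 against Section 7 without them.

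**Conclusion.** The concern holds. A named secondary outcome with a planned repeated-measures analysis has no scheduled measurement at T1, T2 or T3 in either arm. Two of the six distress-scale hypotheses in Aims 1 and 2 have no documented data source, and the same gap affects one DSMB metric and the PTSD alerts. There is no effect on the primary outcome or its power.

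Confidence is high that the written plan contradicts itself. Whether data would actually be lost depends on operational materials that are not available here. If those already contain the PTSS, the correction is to the text only, but it is still needed. This should be fixed, but it does not threaten the main result.

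**What to change.** First establish whether the BLUE CORAL case report forms or the LIFT database already contain the PTSS. Then take one of two courses, before randomisation starts if possible.

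1. **Keep the outcome.** Add the PTSS, with its version, to Table 1 and Section 7.c at T1, T2 and T3 in both arms. The scheduled calls are the simplest route; if another is used, document it. State whether the T1 PTSS is given within the BLUE CORAL interview before LIFT consent, as the PHQ-9 is (Sections 6.b and 8), or after consent and before randomisation. In the second case it may fall as much as 72 hours later (Section 15) and be given by a different team (Sections 6.b and 8), so name who gives it. If some participants have passed T1, collect T2 and T3 and report those comparisons as lacking a baseline value.
2. **Drop the outcome.** Remove PTSD and the PTSS from Aims 1 and 2, Section 10 and the DSMB metrics.

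Under either course, reconcile the alert-value statement in Section 15 with what is measured.

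The cost of the first course is one more questionnaire, of a length the documents do not give, on three existing calls: at most 900 administrations, or at most 660 under the dropout and no-return assumptions above. If the scale is given before LIFT consent, it also falls on interviewees who prove ineligible or decline, a number the documents do not give. It needs agreement with the parent study, which owns the T1 interview. Both courses are protocol changes, reportable under Section 17 to the site IRB, the central IRB and the NIH Program Officer.

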## 4. Study population

### 4.a. BLUE CORAL eligibility

[figure not shown]
Eligible BLUE CORAL patients will be enrolled within 72 hours of hospital admission or COVID-19 confirmation by PCR. Target enrollment is 1,500 patients overall. If enrollment is slow across the Network, alterations may be made in the approach outlined above. Patients or legal next of kin will be approached to engage in the process of informed consent.

#### Inclusion criteria:

1. Adult hospitalized within 14 days of a positive PCR test for COVID-19
2. Evidence of acute COVID-19, with fever or respiratory manifestations, as characterized by signs and symptoms such as cough, dyspnea, tachypnea, hypoxemia, and infiltrates on chest imaging.

#### Exclusion criteria:

1. Lack of informed consent
2. More than 72 hours of continuous hospitalization.
3. Comfort care orders in place at the time of enrollment and/or unexpected to survive for 24 hours
4. Prisoners

## 5. Previous enrollment in BLUE CORAL

### **4.b. LIFT COVID eligibility**

There will be 300 BLUE CORAL patients selected for detailed post-hospital assessment—these will be the target population for the LIFT COVID RCT. If there are more eligible patients, patients may be selected randomly or according to enrichment strategies which will be informed by the composition of the cohort. Informed consent will be obtained by telephone for these potential participants.

Inclusion criteria:

1. Enrolled in BLUE CORAL
2. Survival to hospital discharge
2. English-speaking
3. Domiciled with access to a working telephone and smartphone, tablet, or computer with wifi or internet connection
4. Absence of severe dementia or severe functional disability before hospitalization or at time of 1 month post-discharge interview

Exclusion criteria:

1. PHQ-9 <5 at time of interview 1 month post-discharge
2. Suicidal ideation at time of interview 1 month post-discharge

## 5. Screening

PETAL research staff will identify potentially eligible COVID+ patients hospitalized during the study period using medical records and lists maintained for clinical operations. A log of hospitalized COVID+ patients during the study period will be compiled by participating sites. This log will include simple information: patient name, medical record number, age, sex at birth, date of admission, admission location (ward or ICU), race and ethnicity, and BLUE CORAL enrollment or reason for non-enrollment. This log will be used to describe the relationship between enrolled patients and the larger population. Patient names and medical record numbers from this log will only be used at the local sites and not transmitted to the Clinical Coordinating Center (CCC). Research staff will use the medical records for patients on the log to determine study eligibility. Patient names and medical record numbers will be removed from screening logs, which will then be uploaded by each site into REDCap. This information will be used to describe basic characteristics of the entire population of patients with COVID-19 hospitalized at participating hospitals during the BLUE CORAL study period. If there are multiple patients eligible for BLUE CORAL on a single day, coordinators will prioritize ICU patients first. The screening log will be updated with the results: enrolled, declined, not attempted, ineligible.

## 6. Process of Obtaining Informed Consent

### **6.a. BLUE CORAL**

#### Overview

Prior to conduct of study procedures, informed consent will be obtained from the patient or from a surrogate decision maker if the patient lacks decision-making capacity. In some instances, bringing a paper consent form and pen to the bedside of a patient with known or suspected COVID-19 and then taking these out of the room would violate infection control principles and policies. Given the infectious risk from COVID-19 and potential shortages of personal protective equipment (PPE), there is a moral and practical imperative to minimize face-to-face contact between patients and non-clinical personnel. The current epidemic also presents unique challenges to obtaining consent from participant's legally authorized representative (LAR). To minimize infectious risk, many institutions are not allowing visitors to enter the hospital. Furthermore, the LAR is likely to have been exposed to the patient and may therefore be under self-quarantine at the time of the informed consent discussion.

Therefore, in addition to the traditional approach of an in-person consent discussion and signed paper informed consent document, we will allow use of “no-touch” consent procedures for this trial. Below, we outline two examples of no-touch consent procedures that may be used: (a) a paper-based approach; and (b) an electronic/e-consent approach.

